7.3 Packaging

Bimekizumab and placebo will be packaged and labeled according to Good Manufacturing Practice (GMP) guidelines and applicable laws or regulations. It will be suitably packaged in

such a way as to protect the product from deterioration during transport and storage. Further information regarding storage and transport conditions are provided in the IMP Handling Manual.

7.4 Labeling

Clinical drug supplies will be labeled in accordance with the current International Council for Harmonisation (ICH) guidelines on Good Clinical Practice (GCP) and GMP and will include any locally required statements. If necessary, labels will be translated into the local language.

7.5 Handling and storage requirements

Bimekizumab and placebo must be stored under refrigerated conditions (2°C to 8°C) and protected from light. The study drug must not be frozen.

The Investigator (or designee) is responsible for the safe and proper storage of IMP at the site. Investigational medicinal product stored by the Investigator is to be kept in a secured area with limited access according to the storage conditions mentioned on the label.

Appropriate storage conditions must be ensured by controlling the temperature (eg, room, refrigeration unit) and by completion of a temperature log in accordance with local requirements on a regular basis per study manuals, showing actual and minimum/maximum temperatures reached over the time interval.

Study drug will be shipped to the study sites in temperature controlled containers. Out-of-range shipping or storage conditions must be brought to the attention of the Sponsor or designee, as per instructions contained in the IMP Handling Manual. Authorization to use any out-of-range IMP must be documented and received prior to dispensing or administering the IMP at the study site.

7.6 Drug accountability

A Drug Accountability form will be used to record IMP dispensing and return information on a by-subject basis and will serve as source documentation during the course of the study. Details of any IMP lost, damaged (due to breakage or wastage), not used, partially used, disposed of at the study site, or returned to the Sponsor or designee must also be recorded on the appropriate forms. All supplies and pharmacy documentation must be made available throughout the study for UCB (or designee) to review.

In order to maintain the blind, all IMP documentation (eg, shipping receipts, drug accountability logs, interactive web or voice response system [IXRS] treatment assignments) must be maintained and accessed only by trained unblinded site personnel. Designated unblinded site personnel must be appropriately trained and licensed (per country guidelines) to administer injections.

Blinded study staff may be delegated the responsibility to receive, inventory, and destroy the used kits. The packaging identifies each kit by a unique number that does not correlate to the contents and does not unblind study site staff. Unblinded study staff will be responsible for the preparation (eg, breaking tamper proof sticker on kit) of the IMP, including recording the administration information on the source document.

The Investigator (or designee) is responsible for retaining all used, unused, and partially used containers of IMP until returned or destroyed.

The Investigator may assign some of the Investigator's duties for drug accountability at the study site to an appropriate pharmacist/designee.

The Investigator must ensure that the IMP is used only in accordance with the protocol.

Periodically, and/or after completion of the clinical phase of the study, all used (including empty containers), partially used, unused, damaged, and/or expired IMP must be reconciled and either destroyed at the site according to local laws, regulations, and UCB SOPs or returned to UCB (or designee). Onsite destruction of used kits only may be allowed with prior approval from the Sponsor or designee after reconciliation. Investigational medicinal product intended for the study cannot be used for any other purpose than that described in this protocol.

7.7 Procedures for monitoring subject compliance

During the Treatment Period of this study, study medication will be administered in the clinic and compliance will be determined at the visit by study personnel. Drug accountability must be recorded on the Drug Accountability Form.

7.8 Concomitant medication(s)/treatment(s)

All concomitant medications, including over the counter products, herbal, traditional remedies, vitamin/mineral supplements, other dietary supplements, "nutraceuticals," and hormones must be recorded in the subject's source documentation (eg, clinical chart) and on the eCRF. This record should include the name of the drug, the dose, the route and date(s) of administration, and the indication for use.

The Investigator should examine the acceptability of all concomitant procedures, medications, topical preparations, and dietary supplements not explicitly prohibited in this study, and if necessary, discuss with the Medical Monitor.

In order to ensure that appropriate concomitant therapy is administered, subjects will be instructed to consult with the Investigator prior to taking any medication (either self-administered nonprescription drugs or prescription therapy prescribed by another physician).

7.8.1 Permitted concomitant treatments (medications and therapies)

Topical medications

Subjects may continue to use topical moisturizers or emollients, bath oils, or oatmeal bath preparations for skin conditions during the study, as needed. Over-the-counter shampoos for the treatment of psoriasis of the scalp are also permitted.

Subjects will be allowed to use topical medications (corticosteroids, retinoids, Vitamin D analogs coal tar, etc) as needed during this extension study.

Other medications

Subjects who were already receiving an established nonsteroidal anti-inflammatory drug (NSAID) regimen during PS0010 may continue their use during this study. However, initiation of, or increase in dosage of, NSAIDs during the study (especially in subjects with a history of gastrointestinal [GI] intolerance to NSAIDs or a history of GI ulceration) should be done with caution. Intra-articular injections for arthritis of the knee are allowed.

Subjects who were already receiving an established anti-depressant regimen during PS0010 may continue their use during this study.

7.8.2 Prohibited concomitant treatments (medications and therapies)

The list of prohibited concomitant medications is provided [Table 7-1](#).

Table 7-1: Prohibited psoriasis medications during PS0011

Drug
Systemic retinoids
Systemic treatment (non-biological): systemic immunosuppressant agents (eg, methotrexate, cyclosporine, azathioprine, thioguanine) systemic fumarate systemic corticosteroids phototherapy or chemophototherapy
Anti-TNFs: infliximab (including biosimilar), golimumab etanercept (including biosimilar) certolizumab pegol adalimumab (including biosimilar)
Other biologics and other systemic therapies: apremilast ustekinumab
Anti-IL-17 therapy
Any other antipsoriatic agent (systemic)
Any other antipsoriatic agent (topical) under investigation

IL=interleukin; TNF=tumor necrosis factor

Subjects who take prohibited medications may be withdrawn from study treatment but followed until the SFU Visit. The decision to withdraw a subject for taking prohibited medications should be made in consultation with the Medical Monitor.

Vaccines

Administration of live (including attenuated) vaccines is not allowed during the conduct of the study or for 20 weeks after the last dose of study drug. Administration of inactivated vaccines is allowed during the study at the discretion of the Investigator.

7.9 Blinding

Due to differences in presentation of the IMP (bimekizumab and placebo), special precautions will be taken to ensure study blinding, and study sites will have blinded and unblinded personnel.

Bimekizumab and placebo injections will be prepared and administered at the study sites by unblinded dedicated study personnel who will only be responsible for dosing and drug accountability.

Study sites will be required to have a written blinding plan in place, signed by the Principal Investigator, which will detail the site's steps for ensuring that the double-blind nature of the study is maintained.

During the study, the Sponsor will provide blinded and unblinded site monitors for the purposes of verifying safety, efficacy, and drug administration and documentation records. Blinded study monitors and study site personnel, blinded to treatment assignment, will not discuss or have access to any drug-related information.

When the feeder (PS0010) study is unblinded, selected PS0010 study team members will have access to subject-level data. Because treatment assignment in PS0011 is based on PASI90 response at Week 12 of PS0010 as opposed to randomization, Sponsor personnel with such access to the PS0010 data will know the treatment assignments of all PS0010 subjects including those continuing in PS0011. This operational unblinding to PS0011 treatment assignment will pertain to selected clinical PS0010 study team members (some of whom may be involved in PS0011) but will not extend to blinded staff at the investigational sites of PS0011.

While the blinding of Sponsor clinical study team members is important for ensuring the integrity of data collection and analysis in a controlled study, this unblinding is considered acceptable because the primary evaluation of efficacy, upon which sample size calculations were based, will be performed in a blinded manner using Week 12 data of PS0010. Additionally, because investigational site staff collecting and recording study data remain blinded, those data will not be impacted by the unblinding of selected Sponsor clinical study team members. Finally, to ensure that unblinding of study team members did not impact the primary safety outcome of PS0011, sensitivity analyses will be outlined in the SAP to evaluate what, if any, impact there was on the results based on queries that resulted in changes to the AE data following the unblinding of PS0010.

Further details are provided in the study manuals and site blinding plan.

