14.7 Planned interim analysis and data monitoring

A DMC will review the safety data on a recurring basis as outlined in the DMC charter. In addition to these ongoing reviews, an analysis combining safety data from PS0010 and PS0011 will be performed when the PS0010 study database is locked. This analysis will account for data in PS0010 as well as the accrued safety data in PS0011 available at the time of the PS0010 database lock. At the time of the interim analysis, the DMC will be unblinded; however, the Sponsor study team will remain blind. The details of this combined safety analysis of PS0010 and PS0011, including the events of interest to be considered, will be outlined in the DMC charter.

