1 INTRODUCTION

This statistical analysis plan (SAP) defines the summary tables, figures, and listings to be generated for the clinical study report and is based on the protocol amendment 1 (12 Aug 2016).

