3.11 Changes to protocol-defined analyses

There have been no changes to the protocol-defined analyses.

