4.3 Interim analyses and data monitoring

When PS0010 is unblinded, Sponsor study team members from PS0011 with access to the PS0010 data will be unblinded. However, subjects and investigators will remain blinded. This operational unblinding to PS0011 treatment assignment will pertain to selected clinical PS0010 study team members (some of whom may be involved in PS0011). PS0010 and PS0011 will have the same blinded programming teams for reporting and will remain blinded to PS0010 and PS0011 treatment assignment. An independent programming team will be used for the final unblinding for PS0010 reporting.

A Data Monitoring Committee (DMC) will review the safety data on a recurring basis as outlined in the DMC charter. The outputs reviewed by the DMC will include the accrued data from both PS0010 and PS0011, allowing for summaries of the combined data across the studies. The details of the outputs to be prepared are described in a separate DMC SAP.

An interim analysis focusing on PS0011 only will take place once all subjects have completed the Week 48 visit, but not including the SFU visit. The Clinical Study Report will be updated at a later date in order to incorporate the SFU data once available.

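### The SAP omits the sensitivity analysis of query-changed AE data that Protocol 7.9 promises, the only analytical check it offers on the primary safety outcome after Sponsor unblinding

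*Protocol*

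**What the plan says.** PS0011 treatment follows from the PS0010 arm and the Week 12 PASI90 result, so anyone who sees unblinded subject-level PS0010 data can work out the PS0011 assignment. Protocol 7.9 says this openly, adds that some of the people concerned may work on PS0011, and offers three supports:

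- Efficacy: "this unblinding is considered acceptable because the primary evaluation of efficacy" is carried out blinded, on PS0010 Week 12 data.
- Site blinding: the data are said to be unaffected "because investigational site staff collecting and recording study data remain blinded".
- An analytical check on the main PS0011 safety result: "sensitivity analyses will be outlined in the SAP to evaluate what, if any, impact there was on the results". The object of these analyses is AE records that were altered through queries once PS0010 had been unblinded.

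SAP Section 1 states that the plan rests on protocol amendment 1, the version that carries this promise. SAP 4.3 repeats the unblinding: "Sponsor study team members from PS0011 with access to the PS0010 data will be unblinded". SAP 3.11 reads: "There have been no changes to the protocol-defined analyses".

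Protocol 14.7, on the combined safety analysis at PS0010 database lock, says that "the DMC will be unblinded; however, the Sponsor study team will remain blind".

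**The concern.** The primary safety variable is built entirely from AE records. The protocol recognises that a query raised after PS0010 unblinding can lead to a change in those records, and it hands the SAP the job of showing whether such changes affected the result. If the SAP does not specify the analysis, nobody is bound to run it, and a reader of 3.11 has no sign that anything was left out. The study report could still cite blinded sites and blinded programmers. It could not cite the check that the protocol promised on its own primary outcome.

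**Working it through.** No sample size, power or rate is involved, so the check is a comparison of the two documents.

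1. **Do the other two supports in Protocol 7.9 cover the primary safety outcome?** The first concerns PS0010 efficacy. The second protects the recording of data at the site, but a query reaches the site after the recording. Only the third tests the PS0011 safety result analytically.

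2. **Is the analysis anywhere in the SAP?**
   - 4.3 offers blinded programming teams and an independent team for the PS0010 unblinding. These protect programming and do not address queries.
   - 8.1.1 to 8.1.6 specify one primary analysis: all TEAEs by PS0011 group, SOC, HLT and PT, with counts, EAIR and its interval, and EAER.
   - 8.2.1 adds tables by severity, relationship, seriousness, antibody status, special-monitoring topic and responder status, and combined PS0010 and PS0011 summaries. None compares AE data before and after queries.
   - 12.2 and 12.3 deal with opportunistic infections and anaphylaxis. The contents list shows that 12.1, absent from the public copy, is the SF-36 classification.
   - The amendment log in Section 13 adds nothing of this kind.

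   Promised analyses found: 0. Departures declared in 3.11: 0.

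3. **Is there a route of influence?** Protocol 9.1.9 has a Study Physician or designee review SAEs continuously and reconcile them with patient safety staff. Protocol 13.3.1 has discrepancies between the safety and clinical databases corrected during the study. The documents do not say that the people raising AE queries are the unblinded ones, and they do not exclude it.

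4. **Which AE fields can move the primary table?** From SAP 8.1.4 and 8.1.5, per 100 subject-years:
   - EAIR = 100 × n / ΣT, where n is the number of subjects with the event and T stops at a subject's first event.
   - EAER = 100 × N(AE) / ΣT, where N(AE) counts all events and T is the full time at risk.

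   The inputs are whether a record exists, its start date (treatment emergence and time to first event) and its term (SOC, HLT, PT). Severity, relationship and seriousness on an existing record enter neither formula. There are two side routes. Under Protocol 9.1.5 a worsening is entered as a repeated AE, so a query on severity can add a record. Under SAP 8.1.3 the time at risk of a subject who dies or is lost before Week 48 can depend on the last imputed AE start date.

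A useful check must therefore reverse additions, deletions, and changes of term or onset date.

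**The case against.** Several limits on the point stand.

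- **Unblinded staff do not edit AE data.** A reader might infer that they do. The documents say otherwise: blinded site staff record the data, the Investigator re-approves corrections made after approval, and every change to a saved eCRF needs a reason (Protocol 7.9, 13.3.1). The risk is narrower: a query from someone unblinded prompts a blinded site to change a record. Edits that no query prompted fall outside it, so not every AE record edited after the PS0010 lock is in question.
- **Acceptance of the unblinding does not rest on this analysis alone.** It is the last of three supports, and SAP 4.3 adds blinded programming.
- **SAP 3.11 is not plainly false.** It speaks of analyses defined in the protocol, while Protocol 14.3 does not define this one and 7.9 leaves its design to the SAP. The defect is better called an unmet commitment that 3.11 does not disclose. Nor can 3.11 be taken as assurance. Protocol 14.3.2, for example, shows laboratory and vital-sign changes by PS0010/PS0011 group against both baselines, while SAP 8.2.2 and 8.2.3 use the PS0011 group and PS0011 Baseline only.
- **Protocol 14.7 does not clearly contradict 7.9.** Section 14.7 concerns the interim analysis at database lock and may mean only that the team does not see the DMC output. Section 7.9 concerns selected people once PS0010 is unblinded. Time and persons can differ. The wording is unclear, which is a separate and smaller matter.
- **The study is descriptive and assignment is not randomized** (Protocol 14.2, 7.10). No hypothesis test depends on the missing check.

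None of this supplies the missing analysis. The separate DMC SAP mentioned in SAP 4.3 covers the committee's own outputs, whereas the protocol places this commitment in the SAP.

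**Conclusion.** The point holds in this limited form: Protocol 7.9 commits the SAP to a sensitivity analysis of the primary safety outcome, the SAP acknowledges the unblinding that prompted it, and it neither specifies the analysis nor declares its omission. This should be put right, because a promised check on the primary outcome would otherwise not be run.

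The size is unknown before the audit trail is read. It is tempting to attach a percentage. If one assumed 20 affected subjects in a group and supposed that 1 or 2 of them moved, the numerator would change by 1/20 = 5% or 2/20 = 10%. Those counts are not in the documents. The fractions are also not the change in EAIR, because removing a first event lengthens that subject's time at risk. They should not be read as an estimate.

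The documents do not support a claim that bias occurred or that data integrity was lost. They support the statement that the promised analytical check is absent. The conclusion assumes that no other document binds the sponsor to run the analysis; none is cited for that purpose.

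**What to change.** Add the following to SAP 8.1.6:

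- Fix the PS0010 unblinding date as the date from which Sponsor staff could see unblinded subject-level data.
- Repeat the primary TEAE table (EAIR with interval, EAER) on AE data as they stood before any query raised after that date. Reverse query-driven additions, deletions, and changes to term or onset date, and recompute time at risk where it depends on these.
- Count the changed records by PS0011 treatment group and type of change. The reversal also undoes legitimate corrections, so a difference between the two tables is not in itself evidence of bias. The counts by group are needed to interpret it.
- Apply restored seriousness, severity and relationship only to the 8.2.1 tables that use them.

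If the sponsor decides against the analysis, SAP 3.11 must say so and give the reason.

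The cost is one extra table set and MedDRA recoding of restored terms. Protocol 13.3.2 already provides an audit trail of all saved changes. Linking each change to a query is assumed feasible from the recorded reasons for change, but the documents do not describe that link.

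Separately, clarify in Protocol 14.7 whether the Sponsor team's blindness refers only to the DMC interim output, so that it reads consistently with 7.9 and SAP 4.3. This is a wording change only.

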7.9.1 Procedures for maintaining and breaking the treatment blind

7.9.1.1 Maintenance of study treatment blind

All subject treatment details (bimekizumab or placebo) will be allocated and maintained by the IXRS.

7.9.1.2 Breaking the treatment blind in an emergency situation

The integrity of this clinical study must be maintained by observing the treatment blind. In the event of an emergency for which the appropriate treatment for a subject cannot be made without knowing the treatment assignment, it will be possible to determine to which treatment arm and dose the subject has been allocated by contacting the IXRS. All sites will be provided with details of how to contact the system for code breaking at the start of the study. The Medical Monitor or equivalent should be consulted prior to unblinding, whenever possible.

The Clinical Project Manager will be informed immediately via the IXRS when a code is broken, but will remain blinded to specific treatment information. Any unblinding of the IMP performed by the Investigator must be recorded in the source documents and on the Study Termination eCRF page.

7.10 Randomization and numbering of subjects

No randomization will be performed in this study. An IXRS will be used for assigning eligible subjects to treatment based on a predetermined assignment schedule. An independent biostatistician or designee who is not involved in this study or the feeder study, PS0010, will produce this assignment schedule. Details of the study treatments in PS0011 are presented in [Section 7.2](#).

Subjects will continue with the 5-digit subject numbers assigned by IXRS in the preceding study.

8 STUDY PROCEDURES BY VISIT

[Table 5–1](#) (schedule of study assessments) provides a general overview of study assessments. A list of procedures to be completed at each visit is provided in the sections that follow.

- Visit windows of ± 3 days on either side of the scheduled dosing are permitted for all visits other than the SFU Visit (see below); however, the Investigator should try to keep the subjects on the original dosing schedule. The window of ± 3 days is relative to the first dose (Baseline) and applicable for all subsequent visits. Changes to the dosing schedule outside of the 3-day window must be discussed with the Medical Monitor.
- The minimum time between doses should be no less than 24 days and no more than 32 days for Q4W dosing.
- For the SFU Visit (20 weeks after the last dose of bimekizumab or placebo), the visit should occur no more than 3 days prior to the scheduled visit date and within 7 days after the scheduled visit date (-3 days/+7 days).

